## B2. INNOVATION

This is the **first effort** to provide a theoretically and empirically based smoking cessation treatment in cancer care in Lao PDR. Our mHealth Technology Shared Resource (Director: [name], co-investigator [co-I]) has developed the novel HIPAA-compliant Insight mHealth platform, which enables ecological momentary assessments (EMA) or just-in-time adaptive intervention (JITAI) for various health behaviors or issues. The use of Insight to manage and deliver AT is innovative in several aspects. Insight allows our AT to **function autonomously** and minimizes human involvement, making the approach **affordable for large-scale implementation in LMICs**. Unlike the traditional short message service (SMS) approach that requires an active cellular network connection, our Insight app will automatically deliver all prescheduled interventions and assessments, **with or without an active connection**, thus ensuring timely and reliable treatment delivery. Most importantly, Insight enables complex built-in algorithms and branching logic, allowing us to **create and deliver dynamically and individually tailored treatment content**, using **near real-time EMA data**. Finally, using the friendly, intuitive Insight platform's interface, Lao researchers can directly manage AT whenever and however they wish **without knowledge of programming languages**. Thus, in the subsequent implementation phase of AT or in future cancer survivorship research projects, Lao researchers can **modify the JITAI content to target other behavioral, physical, and psychosocial survivorship outcomes** (e.g., monitoring cancer treatment compliance, fatigue, and complications; providing timely personalized screening recommendations to detect recurrence early; or improving retention in care).

## C2. PRELIMINARY STUDIES

Most relevant to this proposal is our most recent pilot work (with qualitative and quantitative

components) at an HIV clinic in Phnom Penh, Cambodia. We linguistically and culturally adapted the intervention for Cambodian smokers, and then conducted a pilot RCT comparing SC (n=25) to AT (n=25) delivered by our Insight™ platform. Of all scheduled notifications and weekly assessments during the 2-month treatment period, 75% were delivered properly (i.e., the phones were properly charged, turned on, and not lost). Of all delivered messages and assessments, 81% were opened, as indicated by the digital date/time stamp. Retention through the end of the 2-month treatment period, as indicated by returning to the clinic for biochemical confirmation of smoking status (expired CO) was very promising – 100% in the AT group and 92% in the SC group. The **biochemically verified 7-day point prevalence abstinence rate at 2 months was 40% in the AT group and 8% in the SC group** (RR=5.0; 95% CI: 1.2–20.5). The AT group also scored significantly better (p=0.001) on knowledge items about smoking-related health risks and had a greater, but nonsignificant, change in cessation self-efficacy. Most participants agreed that the AT program was helpful in supporting smoking cessation (92%) and would recommend it to other smokers (88%). These data demonstrate the **acceptability, feasibility, reliability, simplicity, and preliminary efficacy of our AT technology in LMICs**. This success suggests that **AT may be appropriate and efficacious in Lao PDR**, a culture comparable to Cambodia.

## D. RESEARCH DESIGN AND METHODS

### Stage 1: Further adapt the AT intervention

[figure not shown]
Before conducting the RCT, we will use a multi-step process to adapt our already developed AT intervention for use by the target populations (i.e., cancer survivors and caregivers). These iterative steps include modifying content, user testing and eliciting feedback, and refining. Specifically, we will review all communication messages in the current AT program and modify them to ensure that they are applicable to cancer survivors and caregivers and to both sexes. Then, we will evaluate the AT content applicability, comprehensibility, and linguistic simplicity and clarity with ~10 cancer survivors or caregivers. We will ensure that approximately half of these testing users are women and that the whole testing sample is demographically diverse. Using input and feedback from these testing users, we will revise the AT further if needed. These series of tests and user-feedback sessions to refine the content further and to debug the system will go through an iterative process as needed. AT content taps on theoretical constructs of the Phase-Based Model (PBM)—a theoretical framework specific to smoking cessation used in our JITAI.

### Stage 2: The pilot RCT

**Participant recruitment.** We will conduct a pilot RCT (N=80) to evaluate the preliminary efficacy of the intervention (*Figure*). Cancer survivors (n=40) or caregivers (n=40) of both sexes who smoke will be recruited from SH and LNCC in Vientiane (the capital of Lao PDR). At SH, the Department of Oncology and Department of Breast and Gynecologic Cancer serve >200 cancer patients each year. LNCC serves >400 new patients with various types of cancer each year. Research staff will review medical records of cancer patients receiving care at the 2 hospitals in the past 2 years, screen for their smoking status documented in the records, and contact those who smoked for further screening. To recruit caregivers, research staff will contact random cancer patients who **did not** smoke and ask if they have a caregiver and if the caregiver smokes. Given the pilot nature of this study, we propose to recruit independent groups of cancer survivors and caregivers who smoke, i.e., no dyads of smokers, to avoid potential interpersonal interactions.

**Inclusion criteria.** The pilot RCT will include those who are 1) aged  $\geq 18$  years; 2) self-reported current combustible cigarette smokers (smoked at least 100 cigarettes in lifetime and currently smoke  $\geq 1$  cigarette/day); 3) willing to set a quit date within 2 weeks of study enrollment; 4) able to provide written informed consent to participate; and 5) able to read Lao (score  $\geq 4$  points on the Rapid Estimate of Adult Literacy in Medicine—Short Form^51). **Exclusion criteria** are 1) history of a medical condition that precludes use of NRT; 2) ineligibility to participate based on medical or psychiatric conditions diagnosed by a physician/clinician; and 3) enrollment in another cessation program or current use of other cessation medications.

**Figure: Study schema**

With these criteria in our Cambodian pilot study, we recruited 2–5 participants per day; thus, we expect a similarly high consent rate and feasibility for this study.

**Baseline assessment.** Enrolled participants will complete a 45-minute baseline self- or assisted interview, managed and delivered by REDCap. Participants will be randomly assigned to SC or AT by the REDCap randomization module (simple, 1:1). Smartphones will be loaned to participants as needed. All participants will complete a brief training session on smartphone use and the Insight app. The Insight app also includes a help button for instructions on how to use each feature, which participants can review at any time.

**Treatment groups.** SC consists of brief advice to quit smoking delivered by research staff, self-help written materials (the WHO’s “A guide for tobacco users to quit” that we have translated to and validated in Lao), and a 2-week supply of NRT (transdermal patches). AT consists of all SC components plus a fully automated smartphone-based JITAI that involves proactive, interactive, and personalized messages, images, or videos in Lao. Adapted from the parent study and based on the PBM, AT content is designed to increase motivation, self-efficacy, and use of coping skills and reduce nicotine withdrawal symptoms and stress. AT will begin immediately after enrollment and continue for 12 weeks (about 2 messages/images/videos per day, delivered at participants’ preferred time). Quit date is set at day 14 post-enrollment for AT and SC participants. JITAI content for AT participants each week will be **personalized and tailored** to each participant’s **baseline information** (e.g., sex, cancer types, caregiver status, and current health conditions), **current PBM phase**, and **responses to the brief weekly EMAs** that drive AT (see *Measures*). Our AT only targets cigarette smoking because it is the most common type of tobacco used by Lao smokers (95%).

**Measures (Table).** **Primary assessments** will be conducted at **baseline and at the 12-week follow-up**, which collect 3 types of data: self-reported data collected by REDCap, expired air carbon monoxide (assessed with Vitalograph BreathCO) to verify smoking status biochemically, and medical record data (for AT personalization). Most of these measures are similar to the parent study and have been translated into Lao. Participants will be compensated US\$15 after completing each of the two primary assessments.

Participants in both groups will be asked to complete **brief weekly assessments** (EMAs)

via Insight app. AT participants will receive 6 PBM-based smoking-related questions (*Table*) that drive JITAI. To balance the effects of these weekly contacts between the RCT groups, we will ask SC participants to complete a weekly 6-item diet EMA. All participants will be provided a prepaid 3-month unlimited data plan. The **primary outcome** is biochemically confirmed (CO level <6 ppm) self-reported 7-day point prevalence abstinence.

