### Abstract

In Lao People's Democratic Republic (Lao PDR), tobacco smoking prevalence among cancer patients is high: 60% in men and 15% in women. Evidence from developed countries suggests that smoking cessation offers considerable benefits for cancer survivors, including improving cancer treatment outcomes, reducing recurrence rates, reducing second primary tumor development, and reducing overall cancer mortality rates. Despite, ***no tobacco treatment programs are available*** in major (public) hospitals in Lao PDR, including in cancer hospitals/institutions. The parent project (1R21CA253600-01, **OUHSC IRB#: 12189**) aims to adapt and evaluate the efficacy of our theoretically and empirically based mobile health (mHealth) technology to help Lao general patients quit smoking cigarettes. This mHealth automated treatment (AT) approach includes a fully automated, interactive, personalized, smartphone-based intervention for behavioral treatment, delivered through our Insight platform. In year 1 of the parent project, we have been adapting our intervention content to the sociocultural context, language, and communication styles of Laotians. The ***purpose*** of this supplementary project is to expand our mHealth-based AT to ***address the pressing need for smoking cessation among cancer survivors and their caregivers in Lao PDR***. In this project, we will adapt our intervention and materials to make them comprehensible and relevant to these target populations. Next, we will conduct a pilot randomized controlled trial (RCT, N=80) to evaluate the preliminary efficacy of the intervention. Cancer survivors (n=40) and caregivers (n=40) of both sexes who smoke will be recruited at Setthathirath Hospital and Lao National Cancer Center. Similar to the parent project's design, participants will be randomized to 1 of 2 treatment groups: standard care (SC) or AT (20 cancer survivors and 20 caregivers in each group). SC consists of brief advice to quit smoking, self-help written materials, and a 2-week supply of NRT (transdermal patches). AT consists of all SC components plus our fully-automated interactive smartphone-based treatment program, personalized and tailored to cancer survivors or caregivers. The ***primary RCT outcome*** is biochemically confirmed self-reported 7-day point prevalence abstinence at 3 months post-study enrollment. The ***specific aims*** are: 1) to evaluate the feasibility of AT in cancer survivors

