and caregivers, and 2) to evaluate the preliminary efficacy of AT in each cancer survivor/caregiver subgroup.

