### A. SPECIFIC AIMS

The specific aims are to:

- **Aim 1:** Evaluate the feasibility of AT in cancer survivors and caregivers. *Hypothesis (H1):*  $\geq 75\%$  of AT content will be viewed/opened as indicated by digital date/time stamp in Insight.
- **Aim 2:** Evaluate the preliminary efficacy of AT in each cancer survivor/caregiver subgroup. *Hypothesis (H2):* At the 12-week follow-up, 7-day point prevalence abstinence will be higher in the AT (vs. SC) group.
- **Aim 3 (capacity building):** Advance mHealth research capacity in Lao PDR and sustain the US-Lao PDR research network by supporting Lao investigators through in-person workshops, in-service trainings, online trainings, manuscript preparation, and future mHealth research collaboration and grant applications.

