### **M. STATISTICAL METHODS**

Descriptive statistics will be used to assess **feasibility** of AT. Regarding **preliminary efficacy** of AT, we will use log-binomial regression with an intent-to-treat approach (i.e., missing=smoking) to compare the effect of the treatment on the dichotomous abstinence outcome at 12 weeks post-enrollment, controlling for selected covariates such as sex, education level, and/or baseline stress level. Secondary outcomes will be examined using appropriate linear and generalized linear mixed models with log-binomial and linear regression for binary and continuous variables, respectively. Given the preliminary nature of the RCT, we do not expect to have sufficient power for full hypothesis testing. However, from our previous work, we anticipate that the abstinence at the 12-week follow-up will be 8% in the SC group. With 40 participants in each group, we will have 80% power to detect a difference as small as 20% in

smoking abstinence rates between groups ( $\alpha=0.05$ , one-tailed, unadjusted).

**Mixed methods data analysis.** At the 3-month follow up assessment, we will use additional open-ended questions at the end of the assessment to explore why and how the participants did or did not successfully quit smoking and stay abstinent. Specifically, for participants who were biochemically confirmed abstinent, the questions will focus on what motivated them to quit and how they overcame challenges or barriers to stay abstinent. For participants who were not abstinent, the questions will focus on why they did not or could not quit, what they underwent, what challenges or barriers they had, and what would help them quit in the future.

Two research team members will perform qualitative data coding with the aid of the R-QDA. Discrepancies will be discussed to achieve intercoder agreement. Codes and quotations will be arranged into focused themes (i.e., thematic content analysis) to develop the mixed methods data inventory. Next, we will examine quantitative (RCT) and qualitative data jointly, using the *integration strategy of explaining* with the intent to explore why participants could or could not quit and stay abstinent. Mixed methods linked data, results, and meta-inferences will be presented in visual joint displays, similar to our previous publication.

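### Simple 1:1 randomisation does not deliver the stated 20 survivors and 20 caregivers per arm, and survivor/caregiver status is neither a stratification factor nor a named covariate

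*Combined protocol and SAP*

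**What the plan says.** The only description of allocation in the readable text is in section D, Stage 2, Baseline assessment: "Participants will be randomly assigned to SC or AT by the REDCap randomization module (simple, 1:1". No section mentions stratification, blocking or minimisation.

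The Abstract gives the cells as "20 cancer survivors and 20 caregivers in each group", without qualification. Section M (Statistical Methods) relies on the matching arm totals: "With 40 participants in each group, we will have 80% power".

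Survivor/caregiver status is the main design factor. Recruitment is set at 40 survivors and 40 caregivers, each with its own route, and Aim 2 in section A is to "Evaluate the preliminary efficacy of AT in each cancer survivor/caregiver subgroup".

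The analysis text (Data analysis in section D, repeated in section M) describes one log-binomial model "to compare the effect of the treatment on the dichotomous abstinence outcome at 12 weeks post-enrollment". Its example covariates are sex, education and baseline stress. The list is open-ended, so status is neither named nor excluded. No subgroup estimate or interaction term is described.

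**The concern.** Three parts of the plan do not fit together: fixed cell sizes, an allocation method that does not fix them, and an aim about subgroups that the described analysis does not address.

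Status is known before randomisation, so balancing on it is easy. Left to chance with 80 participants, the arms can differ appreciably in their mix of survivors and caregivers. If the two groups quit at different rates, that shifts the unadjusted pooled estimate in the trial at hand. It cannot confound a comparison made within one subgroup. There, an uneven split affects only precision and power.

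**Working it through.** **Inputs.** 40 survivors and 40 caregivers (section D, Stage 2); simple 1:1 allocation (Baseline assessment); 8% abstinence on standard care (SC), a 20% difference, one-sided alpha 0.05 and 40 per arm (section M). Assumptions: the 20% is absolute, so 8% v 28%; the same rates apply in both subgroups; *simple* is taken literally.

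**The plan's figures.** The number in the automated treatment (AT) arm from one subgroup is Bin(40, 0.5), with mean 40 × 0.5 = 20 and SD √10 = 3.2. So 20/20 is reproduced as an expectation. At exactly 40 per arm, a pooled-variance z-test has 76.0% power (78.2% by the arcsine formula), slightly below the stated 80%. That gap is a separate matter; 76.0% is the reference here.

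**Chance of the stated cells.**
- One subgroup exactly 20/20: C(40,20)/2^40 = 0.1254. Both: 0.1254² = 0.0157.
- Arms exactly 40/40: C(80,40)/2^80 = 0.0889.
- One subgroup 24:16 or worse, either direction: 2 × P(Bin ≤ 16) = 0.2682. At least one of two: 1 − (1 − 0.2682)² = 0.464.
- One named direction only: 0.1341 per subgroup; at least one of two, 0.250.
- Survivor share differing between arms by 15 points or more (enumeration over two independent Bin(40, 0.5)): 0.219.

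**Average power, fixed v simple allocation.** Pooled: 76.0% to 75.6%. Within a subgroup: 50.1% to 49.2%.

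**Single splits in one subgroup.** Half-width of the 95% CI for the risk difference = 1.96 √(0.08×0.92/n_SC + 0.28×0.72/n_AT). SE of the log risk ratio = √(0.92/(0.08 n_SC) + 0.72/(0.28 n_AT)).

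| SC:AT | Half-width (points) | Power | SE log RR |
|---|---|---|---|
| 20:20 | 23.0 | 50.1% | 0.839 |
| 24:16 | 24.5 | 51.7% | 0.800 (−4.6%) |
| 16:24 | 22.3 | 45.7% | 0.909 (+8.3%) |

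The direction that costs power depends on which arm is short. Averaged over simple allocation, the SE of the log risk ratio rises by 1.2% per subgroup.

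**Shift of the pooled estimate.** Shift = share gap × difference in quit rate by status. The documents give no rate by status. For an assumed difference of 5 to 20 points and a 15-point share gap, the shift is 0.15 × 5 = 0.75 to 0.15 × 20 = 3 points. The pooled CI half-width at 40/40 is 1.96 √(0.0736/40 + 0.2016/40) = 16.3 points.

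**Estimability for Aim 2.** No SC quitters in one subgroup at 20:20: 0.92^20 = 0.189; in at least one subgroup, 1 − (1 − 0.189)² = 0.342. Under simple allocation this is 0.353. At SC rates of 12% and 4% the 20:20 figure is 0.149 and 0.689. With no SC quitters the risk ratio is undefined, while a Newcombe interval for the risk difference stays finite: 6/20 v 0/20 gives 30 points (7.7 to 51.9).

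**A stratified alternative.** Simulated lists of four blocks of 4 and four of 6 in random order, per stratum (4×4 + 4×6 = 40), always end 20:20, with a running difference of at most 3. Guessing the arm that is behind succeeds 69.3% of the time if all earlier allocations in the stratum are seen, about 55% if only the guesser's own hospital's are seen (equal recruitment assumed), and 50% under simple randomisation.

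**The case against.** Simple randomisation is valid, and keeping it in an 80-person behavioural pilot is defensible. The protocol itself disclaims full power, and the 20 per cell can be read as a target. Imbalance moves the pooled estimate by perhaps 0.75 to 3 points against a half-width of about 16. About half of the 24:16 splits improve precision on the risk-ratio scale. A covariate term deals with known imbalance, and the open covariate list already permits one. The missing Aim 2 analysis and the zero-quitter problem do not arise from the randomisation: stratifying changes the zero-cell risk only from 35.3% to 34.2%. Blocking also brings predictability where staff both screen ("Research staff will review medical records of cancer patients receiving care at the 2 hospitals in the past 2 years") and deliver advice ("SC consists of brief advice to quit smoking delivered by research staff").

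Most of this stands, and it is why the point is modest. It does not remove the mismatch: the Abstract states the cells as fact, and the allocation text does not produce them. An open list commits to no adjustment. Adjustment for status also gives no subgroup effects, which Aim 2 requires. Predictability can be limited by varying the blocks and concealing past allocations.

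One reservation remains. The study schema figure and a small part of the text could not be read, so allocation detail given only there would change the point. If the arm totals were in fact fixed at 40/40 without strata, 20/20 would occur in 17.7% of trials, with a central 95% range of 16 to 24 per cell. That is closer, but still not guaranteed.

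**Conclusion.** The concern holds. The stated cells are expected values that the stated method delivers in about 1 trial in 64 (1/0.0157), and the factor defining Aim 2 has no stated role in allocation, adjustment or subgroup estimation. No bias is alleged, and the average power loss is below one point. What is lost is the guaranteed cell sizes and protection of the pooled comparison against chance imbalance on the main design factor. The probabilities rest on literal simple allocation and filled quotas of 40; the power and precision figures also rest on 8% v 28% in both subgroups. The change is worth making because it is cheap, but the trial does not fail without it.

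**What to change.** If enrolment has not begun (the documents do not say):

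1. Replace the simple scheme with 1:1 randomisation stratified by survivor/caregiver status, in concealed permuted blocks of varying size summing to 40 per stratum (for example four of 4 and four of 6 in random order). Keep the list and past allocations from recruiting staff.
2. Include status as a fixed term in the pooled log-binomial model.
3. For Aim 2, report quitters per arm and the treatment effect with a 95% CI in each subgroup. Name a risk difference with a Newcombe interval as the measure, or as the fallback when SC has no quitters.

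If enrolment has begun, or simple randomisation is kept, do items 2 and 3 and restate the counts as about 20 per cell and about 40 per arm. That cures the mismatch but not the chance imbalance.

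The cost is a stratified list in the REDCap module already named and two or three sentences of protocol text. The downsides are the predictability quantified above and one more term in a model with about 14 expected events (40 × 0.08 + 40 × 0.28 = 14.4).

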**Table. Trial Assessments**

Variable type	Measure	BL	W*	12
Descriptors/ potential moderators	Demographics; Health Literacy 	X		X #
	Alcohol and Drug Use 	X		X
	COVID-19–related issues,  co-morbidities 	X		X
	Dependence – Heaviness of Smoking Index 	X		
Feasibility/ Adherence to AT app	Numbers of messages/images/videos opened and completed; weekly assessments opened and completed; activity logs	Date/time stamps in Insight		
Phase-Based Model mechanisms	Wisconsin Smoking Withdrawal Scale 	X		X
	Reasons for Quitting (Intrinsic, Extrinsic) 	X		X
	Contemplation Ladder 	X	X	X
	Kessler Psychological Distress Scale (K10) 	X	X #	X
	Positive and Negative Affect Schedule 	X	X #	X
	Self-Efficacy (related to smoking cessation) 	X	X #	X
Cancer survivorship	Fear of cancer recurrence (survivors only),  family support,  and spiritual well-being 	X		X
Qualitative, open-ended assessment	An in-app participant-initiated assessment—“Share with us anything on your mind”—with an open text field to capture the participant’s thoughts, feelings, and behaviors	Initiated anytime by participant		
Primary outcome	Smoking status in the past week 	X	X #	X
	Expired carbon monoxide at follow-up 	X	X	X
Secondary outcomes	E.g., number of quit attempts, days abstinent, and other tobacco product use 	X		X

Abbreviations: AT, automated treatment; BL, baseline; W, weekly; 12, 12-week follow-up. \**Delivered via Insight app*; \*\**Brief versions of the scales*.

preliminary nature of the RCT, we do not expect to have sufficient power for full hypothesis testing. However, from our previous work, we anticipate that the abstinence at the 12-week follow-up will be 8% in the SC group. With 40 participants in each group, we will have 80% power to detect a difference as small as 20% in smoking abstinence rates between groups ( $\alpha=0.05$ , one-tailed, unadjusted).

